#### **Other-Immune-Mediated Reactions (incl. hypersensitivity reactions)**

Note: As applicable, for early phase studies, the following sentence may be added: "Any event greater than or equal to Grade 2, please discuss with Study Physician." AE: Adverse event; CTCAE: Common Terminology Criteria for Adverse Events; NCI: National Cancer Institute.

Severity Grade of the Event (Refer to NCI CTCAE applicable version in study protocol for defining the CTC grade/severity)	Dose Modifications	Toxicity Management
Any Grade	General Guidance.	
 
For Any Grade
 
Manage per institutional standard at the discretion of Investigator.
 
Monitor patients for signs and symptoms of infusion-related reactions (eg, fever and/or shaking chills, flushing and/or itching, alterations in heart rate and blood pressure, dyspnea or chest discomfort, or skin rashes) and anaphylaxis (eg, generalized urticaria, angioedema, wheezing, hypotension, or tachycardia).
 

Grade 1 or 2	For Grade 1 The infusion rate of investigational drug(s) may be decreased by 50% or temporarily interrupted until resolution of the event.	
 
For Grade 1 or 2
 
Acetaminophen and/or antihistamines may be administered per institutional standard at the discretion of the Investigator.
 
Consider premedication per institutional standard prior to subsequent doses.
 
Steroids should not be used for routine premedication of Grade ≤ 2 infusion reactions.
 

	
 
The infusion rate of investigational drug(s) may be decreased 50% or temporarily interrupted until resolution of the event.
 
Subsequent infusions may be given at 50% of the initial infusion rate.
 
	
Grade 3 or 4	For Grade 3 or 4 Permanently discontinue investigational drug(s).	
 
For Grade 3 or 4
 
Manage severe infusion-related reactions per institutional standards (eg, IM epinephrine, followed by IV diphenhydramine and famotidine, and IV glucocorticoid).
 

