Programmed cell death protein-1 targeting the checkpoint inhibitor axis, PD-1/PD-L1, has a well characterized safety profile with adverse reactions consisting predominantly of imAEs. Such imAEs are well characterized and various internationally recognized management guidelines are available to treat patients experiencing imAEs (Brahmer et al, 2018, Puzanov et al, 2017). The majority of imAEs are low-grade, monitorable, manageable, and reversible with immunosuppressive treatment. Publicly available safety information on anti-TIM-3 antibodies currently in clinical trials indicate- that monotherapy as well as

combination therapy with anti-PD-1 antibodies lead to imAEs which were mainly mild (Grade  $\leq 2$ ). Grade 3 to 4 AEs were reported in approximately 4% to 11% of participants (Borate et al, 2019, Curigliano et al, 2019).

Therefore, imAEs are an important potential risk of sabestomig and include, but are not limited to, pneumonitis, gastrointestinal disorders (especially diarrhea and colitis), hepatitis, endocrinopathies, nephritis and renal dysfunction, skin disorders, encephalitis, myocarditis, and neurological and musculoskeletal inflammatory disorders. Other potential risks include abnormal investigations (changes in laboratory parameters [eg, elevation of amylase, lipase], increased triglycerides and cholesterol, hyperkalemia, hyponatremia), and worsening of existing autoimmune inflammatory conditions.

Further potential risks of sabestomig are immune reactivity (ADA formation potentially leading to development of immune complex disease and vasculitis) and cytokine release syndrome. Like with any other biologic, there are potential risks of IRRs and hypersensitivity reactions.

For more information on the risks of sabestomig administration please refer to the Investigator's Brochure and current version of the TMGs in Appendix I.

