#### Part B Study Stopping Criteria:

During the conduct of Part B, in addition to the stopping criteria applicable for Part A and Part B, the following criteria apply to participants treated at RP2D regardless of the cohort they are enrolled in (Cohort B1, B2 as well as participants treated in Part A mini expansion):

- At the time of interim safety analysis during Part B (after approximately participants have received the first dose at least 3 months prior to data cut-off), the study recruitment may be paused, pending investigation by AstraZeneca in discussion with SRC, if at least one of the following events occur:
  - Incidence of Grade  $\geq$  3 immune-mediated AEs deemed to be related to study drug, above the following limits:
    - $\circ \geq 10$  % participants experiencing Grade  $\geq 3$  pneumonitis
    - $\circ \geq 10$  % participants experiencing Grade  $\geq 3$  myocarditis
    - $\circ \geq 10$  % participants experiencing Grade  $\geq 3$  immune complex disease and vasculitis
    - $\circ \geq 10$  % participants experiencing Grade  $\geq 3$  rash
    - $\circ \geq 10$  % participants experiencing Grade  $\geq 3$  colitis
    - $\circ \geq 10\%$  participants experiencing systemic drug hypersensitivity reactions

- 25% participants discontinuing study treatment due to any grade, treatment-related AE

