#### **Dosing Criteria for Cycles** $\geq 2$

Following completion of the first treatment cycle, participants may receive additional treatment with sabestomig when the following conditions are met:

- The participant does not meet any criteria for discontinuation of IMP as listed in Section 7.1
- The participant has adequate marrow, renal, and liver function, outlined in Table 9. Note: Laboratory evaluations must be performed up to 3 days prior to initiation of each cycle of treatment; transfusion and granulocyte colony stimulating factor support is permissible.
- If the participant experiences an AE following administration of study intervention in the previous dosing cycle, the participant must not meet criteria for dose omission or permanent discontinuation and must meet retreatment guidelines as outlined in the toxicity management guidelines as defined in Appendix I.

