- Renal disorders: Nephritis, nephropathy, elevated serum creatinine, and glomerulonephritis/sclerosis
- Cardiac disorders: Myocarditis and pericarditis
- Skin disorders: Rash, pruritus, dermatitis, vitiligo, psoriasis, SJS/TEN, pemphigus, and lichen planus
- Other rare imAEs including encephalitis, hemophagocytic lymphohistiocytosis, myositis/polymyositis, uveitis, iridiocyclitis, arthritis, Guillain-Barre syndrome, myasthenia gravis, vasculitis, hemolytic anemia, aplastic anemia, anemia, and sarcoidosis

Other aEs which are considered to be AESIs with sabestomig include but are not limited to:

- Infusion-related reactions; hypersensitivity including anaphylactic/anaphylactoid and other allergic reactions
- Immune complex disease and vasculitis
- Cytokine release syndrome

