#### Adapted from Arie Regev, et al., Journal of Autoimmunity, https://doi.org/10.1016/j.jaut.2020.102514

- a Extent and type of work-up may vary by patient's history, severity of liver injury, underlying disease, and geography.
- b Serum AST typically (although not always) is higher than ALT.
- c Acute hepatitis C may be anti-HCV negative but HCV RNA positive.
- d If anti-HEV IgM positive, consider confirmation with HEV RNA by nested PCR.
- e A liver biopsy is needed to confirm a diagnosis of AIH.
- f If cholestatic injury, magnetic resonance cholangiopancreatography may be recommended.
- g Based on medical history and clinical judgment.
- h Alcohol consumption in past 3 to 5 days.
- i Alcohol consumption in past 3 weeks.

Severity Grade of the Event (Refer to NCI CTCAE applicable version in study protocol for defining the CTC grade/severity)	Dose Modifications	Toxicity Management
Any Grade	Note: It is possible that events with an inflammatory or immune mediated mechanism could occur in nearly all organs, some of them are not noted specifically in these guidelines (eg, immune thrombocytopenia, haemolytic anaemia, uveitis, vasculitis).	
 
The study physician may be contacted for immune-mediated reactions not listed in the "specific immune-mediated reactions" section.
 
Thorough evaluation to rule out any alternative etiology (eg,, disease progression, concomitant medications, and infections).
 
Consultation with relevant specialist.
 
Treat accordingly, as per institutional standard.
 

Grade 1	No dose modifications.	Monitor as clinically indicated
Grade 2	
 
Hold investigational drug(s) until resolution to ≤ Grade 1 or baseline.
 
If toxicity worsens, then treat as Grade 3 or Grade 4.
 
Investigational drug(s) can be resumed once event stabilizes to Grade ≤ 1 after completion of steroid taper.
 
Consider whether investigational drug(s) should be permanently discontinued in Grade 2 events with high likelihood for morbidity and/or mortality when they do not rapidly improve to Grade < 1 upon treatment with systemic steroids and following full taper.
 
	For Grade 2, 3, or 4 Treat accordingly, as per institutional standard, appropriate clinical practice guidelines, and other society guidelines (eg, NCCN, ESMO).
Grade 3	Hold investigational drug(s).	
Grade 4	Permanently discontinue investigational drug(s).	

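### Appendix I gives inconsistent Grade 3 dose instructions (hold versus permanently discontinue) for an acute hypersensitivity or anaphylactic reaction around infusion; discontinuation is the better reading, but no text states it

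*Protocol*

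**What the plan says.** Protocol Appendix I sets dose rules by type of event. In the table titled "Other-Immune-Mediated Reactions (incl. hypersensitivity reactions", the Grade 3 row reads "Hold investigational drug(s" and says nothing about whether or when to restart. Permanent discontinuation is a firm instruction only at Grade 4.

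The Infusion-Related Reactions table tells sites, at any grade, to watch for infusion-reaction signs "and anaphylaxis (eg, generalized urticaria, angioedema, wheezing, hypotension, or tachycardia". It suggests intramuscular epinephrine for severe reactions and directs: "For Grade 3 or 4 Permanently discontinue investigational drug(s".

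Four other places bear on the same event:

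- Section 8.3.6 puts "Infusion-related reactions; hypersensitivity including anaphylactic/anaphylactoid and other allergic reactions" in a single bullet of adverse events of special interest, apart from its list of immune-mediated events.
- Section 2.3.1 makes the same pairing: "Like with any other biologic, there are potential risks of IRRs and hypersensitivity reactions".
- Section 4.5 (Part B stopping criteria) places a limit on "participants experiencing systemic drug hypersensitivity reactions" within its list of immune-mediated events.
- Section 6.1.2 (dosing criteria from Cycle 2) says that after an adverse event "the participant must not meet criteria for dose omission or permanent discontinuation and must meet retreatment guidelines" set out in Appendix I.

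**The concern.** A Grade 3 anaphylactic reaction during an infusion is both a hypersensitivity reaction and an infusion-time reaction, so a site can reach either table in good faith. One table ends treatment and the other suspends it. What is at stake is re-exposure of a participant after a severe acute allergic reaction, in a situation where the sponsor's own infusion table says treatment should stop. Hypersensitivity is a named potential risk and an event of special interest in this protocol, so sites should not have to infer the answer.

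**Working it through.** No arithmetic applies. The check sets the two tables side by side and then looks for a rule that decides between them.

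| Feature | Other-immune-mediated table | Infusion-related table |
|---|---|---|
| Names hypersensitivity | Yes, in its title | No |
| Names anaphylaxis | No | Yes, in the any-grade row |
| Grade 3 instruction | Hold | Permanently discontinue |
| Grade 4 instruction | Permanently discontinue | Permanently discontinue |
| Restart condition after Grade 3 | None given | Not applicable |
| Reference to the other table | None | None |

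**Step 1: can one event fall in both tables?** Yes. Section 8.3.6 counts anaphylactic reactions as hypersensitivity, so an anaphylactic reaction at infusion meets the title of the first table and the content of the second.

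**Step 2: where do the tables differ for severe events?** At Grade 3. They agree at Grade 4.

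**Step 3: which text favours discontinuation?**

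- Section 6.1.2 is cumulative. The participant must be clear of every discontinuation criterion and must also meet the retreatment guidance. If the infusion row is met, re-dosing is barred whatever another row says.
- Sections 8.3.6 and 2.3.1 pair hypersensitivity with infusion reactions.
- The general considerations in Appendix I make the other-immune-mediated table a residual one, for immune-mediated events not covered elsewhere. Section 8.3.6 lists hypersensitivity outside those events.
- In the hold table, the Grade 2 row says when drug can be resumed. The Grade 3 row does not.

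**Step 4: which text favours a hold?**

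- The hold table's own title includes hypersensitivity.
- The general rule in Appendix I is to withhold for Grade 3 immune-mediated events, and Section 4.5 lists systemic hypersensitivity among such events.
- Section 6.6.8 asks investigators to consider resuming treatment when symptoms settle promptly with supportive care, as an acute allergic reaction may.

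**Step 5: is there an express rule?** No. Nothing in the protocol or SAP separates hypersensitivity from infusion-related reactions by timing or mechanism, and nothing says that the stricter instruction prevails. Appendix I does draw such boundaries elsewhere. Its neurotoxicity entry excludes myasthenia gravis and Guillain-Barre syndrome, and its amylase/lipase entry sends cases with evidence of pancreatitis to the pancreatitis guidance.

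**The case against.** The strongest reply is that the protocol already decides the outcome. Section 6.1.2 prevents re-dosing once any discontinuation criterion is met, and Section 7.1 lists an event meeting the Appendix I criteria as a reason to stop. Anaphylaxis is named only in the infusion table, so for an event at infusion that is the natural table to use. The hold table can be read without conflict as covering hypersensitivity not tied to an infusion, and a hold is compatible with later discontinuation. Section 4.5 concerns pausing recruitment and is not dose guidance. There are also backstops: immediate safety concerns go to the sponsor to decide on continuation (Section 8), serious events are reported within 24 hours (Section 8.3.9), and the hold table itself calls for specialist consultation.

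Most of this stands, and it is why discontinuation is the better reading. It does not close the gap. Section 6.1.2 refers back to Appendix I without saying which table an event belongs to, so it settles the matter only once the site has used the infusion table. The backstops prompt a conversation and do not supply a dose rule. Section 6.6.8 points the other way when symptoms resolve quickly.

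**Conclusion.** The inconsistency is real and minor. For a Grade 3 acute hypersensitivity or anaphylactic reaction during or shortly after an infusion, Appendix I contains both a hold and a permanent discontinuation. The weight of the text favours discontinuation, but that has to be inferred. This assumes only that some sites may classify such an event by the hold table's title.

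Three stronger readings are tempting and are not supported:

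- A reader might infer that the protocol authorises re-dosing after Grade 3 anaphylaxis. It does not: the Grade 3 hold row gives no permission to resume, and Section 6.1.2 read cumulatively bars it.
- A reader might infer that nothing in the documents bears on the choice of table. Section 6.1.2, Section 8.3.6 and the residual role of the hold table all do.
- A reader might take a frequency from Section 4.3.3, which reports hypersensitivity in 2 of 12 participants, described as having high anti-drug antibody levels, on a PD-L1/TIM-3 bispecific. That is a different molecule and no grade is given, so it says nothing about Grade 3 events with sabestomig. The general 12-week limits on dose delay and steroid reduction do not measure risk here either.

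Design, sample size and planned analyses are unaffected.

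**What to change.** Add one sentence to the other-immune-mediated table: *Acute hypersensitivity or anaphylaxis during or shortly after an infusion is managed under the Infusion-Related Reactions table (permanently discontinue at Grade 3 or 4); this table applies only to hypersensitivity not related to an infusion.*

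This adopts the sponsor's own stricter instruction. The cost is an update to the toxicity management annex, which is kept as a standalone document, and a note to sites. The small downside is that a few participants who might have been re-dosed would stop treatment.

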#### **Infusion-Related Reactions**

CTCAE: Common Terminology Criteria for Adverse Events; IM: intramuscular; IV: intravenous; NCI: National Cancer Institute.

#### Cytokine Release Syndrome (CRS)

NOTE: Dose modification (ie, hold and discontinuation) and toxicity management guidelines for CRS are provided based on 2018 CRS Consensus Grading by Lee et al.

CRS is a systemic inflammatory response caused by the release of cytokines, chemokines and interferon (IFN)-inducible genes that are expected to induce both innate and adaptive immunity. Clinically, CRS consists of a constellation of symptoms that may include fever, nausea, headaches, flushing, flu-like symptoms, tachypnea, hypoxemia, tachycardia, hypotension, confusion, etc, along with possible laboratory changes in the cell blood count, liver function tests, C-reactive protein, and ferritin. Because these symptoms can progress quickly to become potentially life-threatening, suggested guidelines for the management of sabestomig-related CRS are provided below. These general guidelines are to assist the investigator in the diagnosis and management of the potential immune-mediated/CRS events and are not meant to supplant discussions with the Medical Monitor. Accordingly, please notify the Medical Monitor as soon as possible for all AEs consistent with CRS.

Severity Grade of the Event	Dose Modifications	1 oxicity Management		
Grade 1 Fever (≥ 100 °F or ≥ 38°C)*	No dose modifications.	
 
Immediately inform Medical Monitor.
 
Patients should be thoroughly evaluated to rule out any alternative etiology.
 
Symptomatic treatment (eg, antipyretics).
 
Close monitoring of the vital parameters and of biologic lab tests (including CBC, LFTs, CRP, and ferritin) should be performed until resolution of symptoms.
 
		
Grade 2 Fever (≥ 100 °F or ≥ 38°C)* with hypotension not requiring vasopressors and/or hypoxia requiring low-flow nasal cannula or blow-by oxygen	
 
Hold sabestomig until resolution to Grade ≤ 1.
 
If toxicity worsens, then treat as Grade 3 or 4.
 
If toxicity does not improve to Grade ≤ 1 within 48 hours, then permanently discontinue sabestomig.
 
If toxicity improves to Grade ≤ 1 within 48 hours, then sabestomig can be resumed under the following conditions: 
 
The event stabilizes and is controlled.
 
The patient is clinically stable as per investigator or treating physician's clinical judgement.
 
Prednisone equivalent dose is ≤ 10 mg/day.
 
 
 
	
 
Immediately inform Medical Monitor.
 
Recommend hospitalization for management and observation until recovery.
 
Close monitoring of the vital parameters and of biologic lab tests including CBC, LFTs, CRP and ferritin should be performed until the resolution of the symptoms.
 
Aggressive supportive care including fluid and electrolyte replacement.
 
Systemic corticosteroids (1-2 mg/kg/day of methylprednisolone IV) should be considered.
 
Tocilizumab may be considered per the Investigator's institutional SOPs.
 
If the symptoms do not improve within 48 hours despite appropriate medical management, proceed with measures applicable to Grade 3.
 
		
Grade 3 Fever (≥ 100 °F or ≥ 38°C)* with hypotension requiring one vasopressor with or without vasopressin and/or hypoxia requiring high-flow nasal cannula, facemask, non-rebreather mask, or Venturi mask not attributable to any other cause	Permanently discontinue investigational drug(s).	
 
Immediately inform Medical Monitor.
 
Proceed with the CRS management related to Grade 2.
 
Consider higher dose corticosteroids of 1-2 mg/kg every 12 hours of methylprednisolone IV (ie, 2-4 mg/kg/day).
 
		

### **Cytokine Release Syndrome**

Severity Grade of the Event	Dose Modifications	Toxicity Management
Grade 4 Fever (≥ 100 °F or ≥ 38°C)* with hypotension requiring multiple vasopressors (excluding vasopressin) and/or hypoxia requiring positive pressure (eg, CPAP, BiPAP, intubation, and mechanical ventilation) not attributable to any other cause	Permanently discontinue sabestomig.	Immediately inform Medical Monitor. Proceed with the CRS management related to Grade 3.

#### Cytokine Release Syndrome

\*In patients who have CRS then receive tocilizumab or steroids, fever is no longer required to grade subsequent CRS severity. In this case, CRS grading is driven by hypotension and/or hypoxia. BiPAP, bilevel positive airway pressure; CBC, complete blood count; CPAP, continuous positive airway pressure; CRP, C-reactive protein; CRS, cytokine release syndrome; IV, intravenous; LFT, liver function test; SOP, standard operating procedure.

Severity Grade of the Event (Refer to NCI CTCAE applicable version in study protocol for defining the CTC grade/severity)	Dose Modifications	Toxicity Management
Any Grade	Note: Dose modifications are not required for AEs not deemed to be related to study intervention (ie, events due to underlying disease) or for laboratory abnormalities not deemed to be clinically significant.	Treat accordingly, as per institutional standard.
Grade 1	No dose modifications.	Treat accordingly, as per institutional standard.
Grade 2	Hold investigational drug(s) until resolution to $\leq$ Grade 1 or baseline.	Treat accordingly, as per institutional standard.
Grade 3	Hold investigational drug(s) until resolution to $\leq$ Grade 1 or baseline. For AEs that downgrade to $\leq$ Grade 2 within 7 days or resolve to $\leq$ Grade 1 or baseline within 14 days, resume investigational drug(s) administration. Otherwise, discontinue investigational drug(s).	Treat accordingly, as per institutional standard.
Grade 4	Discontinue investigational drugs (Note: For Grade 4 labs, decision to discontinue should be based on accompanying clinical signs/symptoms, the Investigator's clinical judgment, and consultation with AstraZeneca).	Treat accordingly, as per institutional standard.

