#### **Dosing Modification and Toxicity Management Guidelines (TMGs) for Sabestomig**

#### General Considerations Regarding Immune-Mediated Reactions

#### These guidelines are provided as a recommendation to support Investigators in the management of potential imAEs.

Immune-mediated events can occur in nearly any organ or tissue, therefore, these guidelines may not include all the possible immune-mediated reactions. Investigators are advised to take into consideration the appropriate practice guidelines and other society guidelines (eg, NCCN, ESMO) in the management of these events. Refer to the section of the table titled "Other -Immune-Mediated Reactions" for general guidance on imAEs not noted in the "Specific Immune-Mediated Reactions" section. Early identification and management of imAEs are essential to ensure safe use of the study intervention. Monitor patients closely for symptoms and signs that may be clinical manifestations of underlying imAEs. Patients with suspected imAEs should be thoroughly evaluated to rule out any alternative etiologies (eg, disease progression, concomitant medications, infections). In the absence of a clear alternative etiology, all such events should be managed as if they were immune-mediated. Institute medical management promptly, including specialty consultation as appropriate. In general, withhold investigational drug(s) for severe (Grade 3) imAEs. Permanently discontinue investigational drug(s) for life-threatening (Grade 4) imAEs, recurrent severe (Grade 3) imAEs that require systemic immunosuppressive treatment, or an inability to reduce corticosteroid dose to 10 mg or less of prednisone or equivalent per day within 12 weeks of initiating corticosteroids.

Based on the severity of the imAE, treatment with sabestomig should be withheld and corticosteroids administered. Upon improvement to Grade  $\leq 1$ , corticosteroid should be tapered over  $\geq 28$  days. More potent immunosuppressive agents such as TNF inhibitors (eg, infliximab) should be considered for events not responding to systemic steroids. Alternative immunosuppressive agents not listed in this guideline may be considered at the discretion of the Investigator based on clinical practice and relevant guidelines. With long-term steroid and other immunosuppressive use, consider need for *Pneumocystis jirovecii* pneumonia (PJP, formerly known as *Pneumocystis carinii* pneumonia) prophylaxis, gastrointestinal protection, and glucose monitoring.

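### Once Grade 1 CRS fever has been treated with an antipyretic, the Appendix I table cannot grade later hypotension or hypoxia until fever returns or tocilizumab or a steroid is given

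*Protocol*

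**What the plan says.** The CRS table in Appendix I of the protocol ties holding and stopping sabestomig to the CRS grade.

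- **Grade 1** is fever alone. The dose is not modified, and management includes "Symptomatic treatment (eg, antipyretics").
- **Grade 2** is fever "with hypotension not requiring vasopressors and/or hypoxia requiring low-flow nasal cannula or blow-by oxygen". The drug is held. If the event has not improved to Grade 1 or lower "within 48 hours, then permanently discontinue sabestomig" is the instruction.
- **Grade 3** (fever with one vasopressor or high-flow oxygen) and **Grade 4** (fever with several vasopressors or positive pressure) both mean permanent discontinuation.
- **Footnote to the fever criterion:** "In patients who have CRS then receive tocilizumab or steroids, fever is no longer required to grade subsequent CRS severity". Grading then rests on hypotension and hypoxia.

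Within the table, steroids and tocilizumab first appear in the Grade 2 row, as options to consider. Nothing else in the CRS section waives fever.

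For events outside the named tables, the General Considerations in Appendix I say: "In the absence of a clear alternative etiology, all such events should be managed as if they were immune-mediated". The row for other immune-mediated reactions holds the drug at Grade 2 and adds: "Investigational drug(s) can be resumed once event stabilizes to Grade" 1 or lower, after any steroid taper. It also says: "Consider whether investigational drug(s) should be permanently discontinued in Grade 2 events with high likelihood for morbidity and/or mortality". At Grade 3 it holds the drug, and at Grade 4 it stops it.

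**The concern.** The Grade 1 row names a treatment that removes fever, every higher grade needs fever, and the waiver leaves that treatment out. The table can therefore lose track of a participant who is getting worse because its own first-line measure has worked on the fever.

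Appendix I warns that CRS symptoms can progress quickly and become life-threatening, and the 48-hour and Grade 3 stops are the table's protection against re-exposure. If worsening cannot be graded as CRS, those stops do not fire from the table, and the event is handled under a row that has no 48-hour limit.

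**Working it through.** No figure in the plan bears on this point, so the check applies the table as a rule.

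**Inputs**, all from the Appendix I CRS table and footnote:
- F: fever is present.
- W: the waiver is open (CRS, then tocilizumab or steroid).
- H: hypotension and/or hypoxia at the level of the row.

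**Rule:** CRS Grade 2 to 4 = (F or W) and H. Grade 1 = F without H.

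| Situation | F | W | H | CRS grade |
|---|---|---|---|---|
| Fever with hypotension or hypoxia | yes | no | yes | 2 to 4 |
| Grade 1 CRS, antipyretic only, afebrile, then hypotensive or hypoxic | no | no | yes | none, not even 1 |
| Same participant, fever returns | yes | no | yes | 2 to 4 |
| Same participant, tocilizumab or steroid given | no | yes | yes | 2 to 4 |

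The second line is the gap. The third and fourth lines show the two ways it closes.

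**Worked example.** Hypotension not needing vasopressors begins on Day 1 in a participant whose CRS fever has gone on an antipyretic. It recovers at 72 hours, and no steroid or tocilizumab is given.

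- *If CRS Grade 2 applied:* 72 h exceeds the 48 h limit by 72 − 48 = 24 h, so treatment has been permanently stopped.
- *Under other immune-mediated reactions, Grade 2:* the drug is held until Grade 1 or lower, or baseline. Discontinuation is only to be considered, for high-risk events that do not improve rapidly. With no steroid given, there is no taper to wait for.
- *Under the same row, Grade 3:* the drug is held. The General Considerations add a mandatory stop for recurrent Grade 3 events needing systemic immunosuppression, or when steroids cannot be reduced to 10 mg/day or less within 12 weeks. Neither applies to a first event without steroids.

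On the three-weekly schedule the next dose falls on Day 1 + 21 = Day 22. At Grade 2 or 3 the fallback row does not by itself require discontinuation before then. The outer limit for treatment-related toxicity is Section 6.7: more than 12 weeks without drug.

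At fallback Grade 4 both rows stop treatment, so there is no contrast.

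**The case against.** The strongest reply is that the table does not work alone.

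- Appendix I calls its guidelines recommendations. It asks for Medical Monitor notification of every event consistent with CRS and, already at Grade 1, for close monitoring until symptoms resolve.
- Section 6.6.8 interrupts dosing for clinically significant toxicity. Section 7.1 allows discontinuation for any adverse event that the investigator or sponsor thinks warrants it. The dosing criteria for Cycles 2 onward in Section 6.1.2 must be met before re-dosing.
- The General Considerations that lead to the fallback row also call for corticosteroids according to severity, and one steroid dose opens the waiver.
- The infusion-related reaction table is another plausible home for hypotension after an infusion, and it stops treatment at Grade 3 or 4.

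All of this stands, and it reduces the risk. None of it assigns a CRS grade or triggers the 48-hour stop.

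A second reply is that the table follows a published consensus scale. That source is not in the documents, so whether the footnote departs from it cannot be settled here. The mismatch between the Grade 1 treatment and the footnote lies within the protocol's own table.

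Several stronger readings are tempting but not supported:

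- *That the participant is trapped.* A reader might infer this because the waiver drugs first appear at Grade 2. But Section 6.5.2 lists tocilizumab as rescue medication without a grade or fever condition, and Table 12 allows immunosuppressants for treatment-related events.
- *That hypotension needing one vasopressor is also handled more leniently.* The fallback row uses CTCAE grades. Under the general definitions in Appendix D 2, such an event could be Grade 4, which stops treatment there too.
- *That Part A dose-limiting toxicities would be missed.* Section 6.6.3 uses CRS grades without naming the scale. Section 6.6.8 refers to CTCAE v5.0, whose CRS text is not reproduced.
- *That routine Section 6.5.1 premedication masks CRS.* The point does not rest on this. It concerns recognised CRS treated under the Grade 1 row.

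**Conclusion.** The point holds as a limited safety clarification. On the wording of Appendix I, a participant whose Grade 1 CRS fever has resolved on an antipyretic and who then becomes hypotensive or hypoxic has no CRS grade until fever returns or tocilizumab or a steroid is given. While that lasts, the table does not trigger the Grade 2 48-hour stop or the Grade 3 stop.

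The size is best stated by the one firm contrast: mandatory discontinuation at 48 hours against a hold with no required discontinuation. It assumes that fever stays away, that no steroid or tocilizumab is given, and that the event is graded 2 or 3 under other immune-mediated reactions. It does not show that the participant would in fact be re-dosed, because the other safeguards still apply.

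The documents give no frequency for this sequence. Section 2.3.1 rates the CRS risk as low, so it is expected to be uncommon. No endpoint, sample size or error rate is affected. The change is worth making because a table that sets permanent-stop rules should be able to grade worsening after its own first-line treatment.

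**What to change.** Amend the footnote to the CRS table in two ways:

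1. Extend the list of drugs that open the waiver to *antipyretics, tocilizumab or steroids for that CRS event*.
2. Add: *Premedication or scheduled post-infusion acetaminophen/paracetamol under Section 6.5.1 alone does not open this waiver.*

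The second sentence is needed because every participant receives paracetamol before each dose and may receive it at 4, 8 and 12 hours afterwards. Without it, routine premedication could be taken to open the waiver. No new data field is required: Section 6.5 already records the reason, dates and dose of concomitant medication, and Section 6.5.2 the date and time of rescue medication.

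The Grade 2 definition should stay as it is. It lacks the attribution wording that ends the Grade 3 definition ("Venturi mask not attributable to any other cause"), but adding that wording would not repair this gap and would narrow an existing safety stop.

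Costs: slightly more events may be graded CRS Grade 2 or higher. A participant whose CRS fever is suppressed only by scheduled Section 6.5.1 paracetamol remains outside the waiver and depends on the investigator and the Medical Monitor. The annex is versioned separately from the protocol, but its substantial updates go through submission and approval, and Appendix L lists earlier changes to the CRS guidance as substantial. The edit is short, but it may need regulatory submission.
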